I understand that the Sponsor may decide to suspend or prematurely terminate the study at any time for whatever reason; such a decision will be communicated to me in writing. Conversely, should I decide to withdraw from execution of the study, I will communicate my intention immediately in writing to the Sponsor.

_____ Print Name	_____ Signature
_____ Investigator Title	_____ Date (DD MMM YYYY)

PROTOCOL SYNOPSIS

Protocol Number:	ALT-FLZ-401
Product:	Fluzone Intramuscular Quadrivalent vaccine
Active Ingredient(s)/INN:	Vaccine
Study Title:	Extent and Durability of Immune Response Following Seasonal Influenza Vaccination in Healthy Volunteers
Study Phase:	Phase 4
Indication Under Investigation:	Influenza
Study Objectives:	
Primary Objective
 
To evaluate antibody response against matched influenza strains as measured by hemagglutination inhibition (HAI) following administration of a seasonal influenza vaccine.
 
Secondary Objectives
 
To evaluate 1) antibody responses to divergent influenza strains 2) cellular immune responses and 3) mucosal antibody responses following administration of seasonal influenza vaccine (Fluzone Quadrivalent)

Study Design:	
This will be an open-label, single administration dose study in adult healthy male and female subjects. After qualifying for the study, subjects will receive a single intramuscular injection of the FDA approved 2016-2017 quadrivalent influenza vaccine.
 
Subjects will be screened within 28 days prior to enrollment into the study. After qualifying for the study subjects will visit the clinical unit on Day 1 and will have pre-dose blood samples taken for humoral (serum) and cellular (peripheral blood mononuclear cells PBMCs) immunity testing and nasopharyngeal swabs for assessment of mucosal immunity, and will then be given the vaccine. Over the next 6 months, 10-mL blood samples will be collected on Days 4, 8, 15, 29, 91 and 181 for HAI testing. Peripheral blood mononuclear cells will be collected on Day 8 to assess cellular responses. A nasopharyngeal swab will also be done on Day 29. Screening assessments will include clinical laboratory tests (hematology, chemistry, urinalysis

	[UA], drug and alcohol testing), vital signs, 12-lead electrocardiogram and physical examination. Adverse events (AEs) will be monitored throughout the study.

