3.1.4. Duration of the Study

The duration of the study will be approximately up to 7 months.

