NCI	New-onset Chronic Illness
PBMC	Peripheral Blood Mononuclear Cells

Abbreviation/Term	Definition
PP	Per-protocol
PT	Preferred Term
qPCR	Quantitative Polymerase Chain Reaction
SAE	Serious Adverse Event
SAP	Statistical Analysis Plan
SCR	Seroconversion Rate
SD or sd	Standard Deviation
SDTM	Study Data Tabulation Model
SFU	Spot-forming Unit
SOC	System Organ Class
SPR	Seroprotection Rate
SRC	Safety Review Committee
TEAE	Treatment Emergent Adverse Event
TFL	Tables, Figures, and Listings
vp	Viral Particles
WHO	World Health Organization

SUMMIT ANALYTICAL

2 Introduction

This document presents a statistical analysis plan (SAP) for Altimune, Inc. Protocol ALT-103-201, Single-ascending-dose Study of the Safety and Immunogenicity of NasoVAX.

Reference materials for this statistical plan include the Protocol ALT-103-201 Version 4.0 (dated 05 October 2017) and Electronic Case Report Forms (eCRF) (dated 02 September 2017).

Additionally, this plan incorporates a previous Phase 4 study of licensed seasonal vaccine in a similar subject population, ALT-FLZ-401, Extent and Durability of Immune Response Following Seasonal Influenza Vaccination in Healthy Volunteers. The reference materials for the comparison study include the Protocol ALT-FLZ-401 Version 1.0 (dated 26 April 2017) and eCRF (dated 02 May 2017). Disposition, demographic, and immunogenicity data from ALT-FLZ-401 will be included in the summaries described below.

The statistical plan described hereafter is an *a priori* plan. It will be submitted to file prior to any unblinded inferential or descriptive analyses of data pertaining to the Altimune, Inc. study ALT-103-201. This statistical plan disallows any analyses to be performed for any purpose prior to the unblinding of final study data and the submission to file of the final version of this plan. SAS programming may occur as study data accumulate in order to have analysis programs ready at the time the study finishes. In such an event, arbitrary dose group assignments must be randomly linked to subjects, effectively rendering any output of programs meaningless. For the reasons stated here the conduct of the study in the field is considered to be independent of any study outcome that might materialize upon enactment of the currently proposed statistical plan.

SUMMIT ANALYTICAL

3 Study Objectives and Endpoints

OBJECTIVES	ENDPOINTS
Primary Objective	

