All AEs and medications will be recorded from signing of the informed consent form to Day 29. Thereafter to the end of the study, only MAEs, NCIs, SAEs, immunosuppressive medications (see list in Appendix 3), and vaccines will be recorded. Samples for clinical laboratory tests (hematology, serum chemistry, urinalysis) will be collected at Screening and on Days 8 and 29. A complete physical examination and vital signs will be performed at Screening and predose on Day 1, and targeted and symptom-driven physical examinations will be performed and vital signs measured 2 hours postdose and on Days 4, 8, 15, and 29. An electrocardiogram (ECG) will be performed at Screening and on Day 29. If a subject experiences acute symptoms compatible with adenoviral infection within 28 days after the NasoVAX/placebo dose, a sample will be collected for viral culture as clinically indicated.

One interim analysis of humoral immunogenicity data and safety data (including summaries of AE, reactogenicity, concomitant medications and vaccines, vital signs, ECG, and laboratory data and listing of any viral culture results) will be conducted when all data through the Day 29 visit is available and monitored for all subjects.

A complete schedule of procedures and assessments for study ALT-103-201 is in Table 4-2.

ALT-FLZ-401, Extent and Durability of Immune Response Following Seasonal Influenza Vaccination in Healthy Volunteers, was an open label study designed to generate an immunogenicity sample set similar to that of ALT-103-201 in subjects receiving a licensed influenza vaccine based on the same H1 strain (A/California 2009). The seasonal vaccine H1 component changed at the time of the ALT-103-201 study to A/Michigan, so it was logistically much easier to conduct this study non-contemporaneously with the seasonal vaccine licensed for use in 2016-17. The same site, entry criteria and schedule of assessments for immunogenicity were followed. Twenty subjects were enrolled and samples from this study were frozen and stored and then shipped to blinded laboratory for immunogenicity testing in parallel to the samples from ALT-103-201. The schedule of events for ALT-FLZ-401 is in Table 4-3.

Table 4-2. ALT-103-201 TIME AND EVENTS SCHEDULE

Study Visit	Screening	Dosing Period							Follow-up Period	
		Day 1		Day 2 ^a	Day 4	Day 8	Day 15	Day 29	Day 91	Day 181
Window (days)	Day -28 to Day -1	Predose	Postdose		± 1	± 1	± 1	± 3	± 10	± 10
Informed consent	X									
Demographics	X									

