8.6 Immunogenicity Analysis

All immunogenicity analyses will be conducted on the PP Population. Analyses based on the ITT Population will be undertaken and presented only if >5% of subjects in any 1 dose group were excluded from the PP Population. Summaries and analysis will be completed by dose group and overall for subjects on an active NasoVAX dose.

The variables that will be analyzed, and the endpoints generated for each variable, are listed in Table 8-1:

Table 8-1. Immunogenicity Variables and Endpoints

Variable Name	GMT	GMR	SPR	SCR	Responder Rate	Geometric Mean SFUs	Compare to ALT-FLZ-401
A/California 2009 antibody level measured by HAI in serum	X	X	X	X			X
A/California 2009 antibody level measured by MN in serum	X	X			X		X
Cellular response to A/California 2009 peptides measured by enzyme-linked ELISpot in PBMCs					X	X	X
IgA antibody level measured by ELISA in nasopharyngeal swab	X	X					X
Antibody level measured by HAI in serum against the following nonrepresented strains: - A/Brisbane/59/2007 (H1 strain) - A/Saint-Petersburg/61/2015 (H1 strain) - A/New Jersey/76 (H1 strain) - A/Perth/16/2009 (H3 strain) - A/Vietnam/1203/2004XPR8 (H5 strain)	X	X			X		X
Antibody level measured by MN in serum against nonrepresented strains	X	X			X		X
Ad5 antibody levels in serum	X	X			X		

Note: Refer to Section 3 for descriptions of each endpoint.

Assay data will be tabulated by visit using the applicable endpoint(s) (e.g., GMT, GMR, or geometric mean SFUs) and their 95% CIs. Graphical representations of the longitudinal immune responses will also be given.

[figure not shown]
Analysis of covariance (ANCOVA) will be used in the analysis of the antibody levels at each post-baseline visit, with log-transformed antibody level as dependent variable, dose group as a factor, and baseline log-transformed level as a covariate. This model will be generated using SAS Proc Mixed with dose group in the CLASS statement and visit in the BY statement. Comparisons of post-baseline log-transformed antibody level will be conducted for each NasoVAX dose group against the placebo group and against the Fluzone group, if applicable. Least square (LS) means and 95% CI of the LS means of dose group, difference of LS means and 95% CI of the difference in LS means will be

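### The NasoVAX-versus-Fluzone HAI tests at Days 91 and 181 mix vaccine durability with different calendar exposure and should be descriptive only

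*SAP*

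**What the plan says.** SAP Section 4 explains that the Fluzone study was run separately, using the 2016-17 vaccine, so that its H1 strain would match: "The seasonal vaccine H1 component changed at the time of the ALT-103-201 study to A/Michigan", and so "it was logistically much easier to conduct this study non-contemporaneously with the seasonal vaccine licensed for use in 2016-17". SAP Section 7.4 nevertheless makes the Fluzone subjects an extra arm for immunogenicity. Section 7.4 also sets two-sided 0.05 tests without multiplicity adjustment.

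Both studies draw serum for A/California HAI late in follow-up. For ALT-FLZ-401 the Protocol synopsis says "10-mL blood samples will be collected on Days 4, 8, 15, 29, 91 and 181 for HAI testing", and SAP Section 4 gives the same days for ALT-103-201. Section 8.6 fits an ANCOVA at each post-baseline visit, with dose group and baseline log titer as the only terms: "Comparisons of post-baseline log-transformed antibody level will be conducted for each NasoVAX dose group against the placebo group and against the Fluzone group". It adds score intervals and Fisher's exact tests for seroprotection and seroconversion, and restricts none of these to early visits.

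The only dates are document dates, in SAP Section 2: for Fluzone, "Protocol ALT-FLZ-401 Version 1.0 (dated 26 April 2017) and eCRF (dated 02 May 2017"); for NasoVAX, "Protocol ALT-103-201 Version 4.0 (dated 05 October 2017) and Electronic Case Report Forms (eCRF) (dated 02 September 2017"). Neither document gives a first-dose, last-dose or visit date.

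**The concern.** An HAI titer at Day 91 or Day 181 reflects what is left of the vaccine response plus anything that raised antibody since, such as natural infection or another influenza vaccine. When arms run concurrently, that second part is shared on average. Here it is not. The baseline covariate is measured before dosing and cannot correct for exposure after dosing. Running the assays together with the laboratory blinded to study (SAP Section 7.4.2) deals with assay drift, not exposure.

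The ALT-103-201 placebo group shows background change in its own period, but ALT-FLZ-401 has a single treatment group (Protocol Section 3.1.2), so its background change cannot be estimated.

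Clinical records help only in part. In ALT-103-201 all adverse events are recorded to Day 29; "Thereafter to the end of the study, only MAEs, NCIs, SAEs, immunosuppressive medications" and vaccines are then kept. ALT-FLZ-401 monitors adverse events at every visit to Day 181. Neither schedule of events lists an influenza test. Vaccines are recorded in both studies (Protocol Section 5.5; SAP Section 4), but no rule says what to do with sera drawn after one.

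At stake is how the late results are read: a difference in season could be reported, with a p-value, as a difference in durability.

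**Working it through.** The plan gives no figure for this comparison. The Fluzone sample size was set on practical grounds, and the probabilities in SAP Section 7.1 concern adverse events.

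**Number of affected contrasts.** 3 doses x 2 late visits x 3 HAI endpoints (GMT, seroprotection, seroconversion) = 18. Under SAP Section 4, microneutralization, nonrepresented-strain HAI, ELISpot and IgA are not measured after Day 29, so only A/California HAI is affected.

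**Calendar.** Visit date = dose date + (visit day - 1). Every dose date below is an assumption anchored on the document dates.

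| Assumed dose date | Day 29 | Day 91 | Day 181 |
|---|---|---|---|
| Fluzone, 26 Apr 2017 (protocol date) | 24 May | 25 Jul | 23 Oct 2017 |
| Fluzone, 30 May 2017 | 27 Jun | 28 Aug | 26 Nov 2017 |
| Fluzone, 30 Jun 2017 | 28 Jul | 28 Sep | 27 Dec 2017 |
| Fluzone, 31 Aug 2017 | 28 Sep | 29 Nov | 27 Feb 2018 |
| NasoVAX, 2 Sep 2017 (eCRF date) | 30 Sep | 1 Dec | 1 Mar 2018 |
| NasoVAX, 5 Oct 2017 (protocol v4.0 date) | 2 Nov | 3 Jan 2018 | 3 Apr 2018 |

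Each NasoVAX cohort waits for Day 8 of its sentinels and then Day 8 of the remainder, so 7 + 7 = 14 days per cohort. The top dose starts at least 28 days after the first dose. From 2 September that is 30 September, giving Day 91 on 29 December 2017 and Day 181 on 29 March 2018.

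**Overlap.** With Fluzone doses from 26 April to 30 June and the ±10-day windows, Fluzone Day 91 spans 15 July to 8 October 2017, and NasoVAX Day 91 starts on 21 November. Fluzone Day 181 spans 13 October 2017 to 6 January 2018, and NasoVAX Day 181 starts on 19 February. Each gap is 44 days. It closes if Fluzone dosing ran to 13 August (30 June + 44 days) or NasoVAX dosing began on 20 July (2 September - 44 days).

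The Protocol gives soft support for early Fluzone dosing: "The duration of the study will be approximately up to 7 months" (Section 3.1.4). Seven months from 26 April or 2 May ends on 26 November or 2 December 2017. But Section 3.1.5 gives the same length for one subject, which leaves no time for accrual. A Fluzone dose after 23 June puts Day 181 on or after 21 December, so a seasonal contrast at that visit is not secure.

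**Scale, illustration only.** No infection or vaccination rate is in the documents. If k of n subjects have an F-fold rise, the group GMT is multiplied by F^(k/n).

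- NasoVAX dose group, n = 15, F = 8: 8^(1/15) = 1.15 for one subject and 8^(2/15) = 1.32 for two.
- Fluzone group, n = 20, F = 8: 8^(1/20) = 1.11 and 8^(2/20) = 1.23, so the NasoVAX:Fluzone ratio is multiplied by 0.90 or 0.81.

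A simulated two-group ANCOVA (15 versus 20, equal true durability, rises in NasoVAX only, log-titer SD 0.8 to 1.4, baseline correlation 0.6, 4,000 runs per setting) rejects at these rates:

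| Assumed share boosted, fold rise | Rejection rate of one nominal 5% test |
|---|---|
| none | 4.8% to 5.4% |
| 5%, 4-fold | 5.6% to 6.2% |
| 10%, 4-fold | 6.0% to 8.4% |
| 20%, 4-fold | 9.8% to 18.3% |
| 20%, 8-fold | 15.4% to 27.6% |

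On the same assumptions the 95% CI for the ratio has a half-width factor of exp(2.037 x SD x √(1 - 0.6²) x √(1/15 + 1/20)), which is 1.56 at SD 0.8 and 2.18 at SD 1.4.

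**The case against.** The strongest reply is that the comparison is an exploratory objective (SAP Section 3), that the SAP discloses the separate timing and gives a sound reason for it (matching the H1 strain), and that placebo titers will be tabulated and plotted by visit, so a reader can see background drift. Modest exposure would also be hard to tell from noise: shifts of 1.15 or 1.32 lie within the assumed interval width, and the 5% and 10% scenarios barely raise the error rate. All of this stands and limits the weight of the point. It does not supply a background estimate for the Fluzone period, and it does not make a late p-value interpretable as durability.

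A reader might infer more: that the two follow-ups are shown to sit in opposite seasons, and that winter infection props up NasoVAX titers while Fluzone wanes. The documents do not support that. The seasons come from protocol and eCRF dates. An eCRF version date does not bound first dosing, particularly when the protocol is already at Version 4.0. Even with dosing ending in June, Fluzone Day 181 could fall as late as 27 December. There are no data on virus circulation in either period, and an off-study influenza vaccine taken before Fluzone Day 181 would push the other way.

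Nor can it be said that infections are clinically invisible. Medically attended events are recorded to Day 181 in ALT-103-201, and that study's own protocol is not among the documents.

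**Conclusion.** The point holds as a confounding problem of unknown size and direction. Non-concurrent groups are tested against each other at Days 91 and 181 as though they were arms of one trial, and nothing in the model or data handling separates durability from exposure after dosing. That follows from the SAP's own text and needs no assumed dates.

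The probable contrast at Day 91, summer to early autumn against December or later, rests on dosing having followed the document dates and on Fluzone dosing ending by about June 2017. Day 181 is less certain.

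The primary objective is unaffected. NasoVAX versus placebo is concurrent, and Fluzone contrasts through Day 29 are less exposed because only 28 days have passed since dosing. It is a worthwhile correction to an exploratory analysis, not a threat to the study's main conclusions.

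**What to change.** In SAP Section 8.6:

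1. Present NasoVAX and Fluzone HAI results at Days 91 and 181 descriptively: estimates and CIs by group, the actual range of visit dates, no p-values and no claim about relative durability. Keep inferential Fluzone comparisons to visits through Day 29.
2. Base late conclusions about NasoVAX on the concurrent placebo contrast. Print the placebo Day 91/Day 29 and Day 181/Day 29 GMRs beside the late Fluzone summaries, as the measure of background change in the NasoVAX period.
3. As a labelled sensitivity analysis only, repeat the late summaries in all groups without sera drawn after a recorded off-study influenza vaccine, or from a 4-fold or greater HAI rise after Day 29 onward. State that the titer-based exclusion depends on the outcome and lowers late GMTs: it also removes genuine late responses and assay variation near the quantification limit, for example 5 (the imputed value) to 20.

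The cost is SAP wording, one derived flag and visit dates; no new samples are needed. The loss is p-values for an exploratory contrast at two visits.

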7. Clinically significant ECG abnormality
8. Poorly controlled hypertension (systolic blood pressure $> 150 \text{ mmHg}$ or diastolic blood pressure $> 95 \text{ mmHg}$) at Screening or predose on Day 1
9. History of anaphylaxis or angioedema
10. Known allergy to any of the ingredients in the vaccine formulation, including egg allergy
11. History of chronic rhinitis, nasal septal defect, cleft palate, nasal polyps, or other nasal abnormality that might affect vaccine administration
12. Previous nasal surgery or nasal cauterization
13. Any symptoms of upper respiratory infection or temperature $> 38^\circ\text{C}$ within 3 days before Day 1
14. Significant nasal congestion or rhinorrhea as assessed by the investigator.

15. Known or suspected malignancy, excluding non-melanoma skin cancers and other early stage surgically excised malignancies that the Investigator considers to be exceedingly unlikely to recur
16. Immunocompromised individuals, including those who have used corticosteroids (including intranasal steroids), alkylating drugs, antimetabolites, radiation, immunomodulating biologics, or other immunomodulating therapies within 90 days before Day 1 or those who plan use during the study period
17. Use of statin medication within 30 days before Day 1 (including atorvastatin, fluvastatin, lovastatin, pravastatin, rosuvastatin, simvastatin, pitavastatin)
18. Receipt of intranasal medications (including over-the-counter medications) within 30 days before Day 1
19. Receipt of any IP within 30 days before Day 1
20. Receipt of any vaccine within 30 days before Day 1
21. Receipt of intranasal vaccine within 90 days before Day 1
22. Receipt of any influenza vaccine within 6 months before Day 1
23. Any change in medication for a chronic medical condition within 30 days before Day 1
24. Past regular use or current use of intranasal illicit drugs, or any illicit drug by any route
25. Use of tobacco products or electronic cigarettes within 30 days before Day 1, or smoking of any type, including marijuana
26. Any medical, psychiatric, or social condition or any occupational or other responsibility that in the judgment of the Investigator would interfere with or serve as a contraindication to protocol adherence, assessment of safety (including immunogenicity), or a subject's ability to give informed consent

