6.3 Treatment Period

6.3.1 Day 1

Subjects will check in to the clinic approximately 30 minutes to 1 hour before study procedures for pre-dose assessments. The following procedures will be performed:

- All subjects will be questioned to affirm that the inclusion and exclusion criteria/restrictions have not been violated since Screening ([Section 4](#)).
- All WOCBP will undergo a urine pregnancy test; negative results must be obtained for eligibility
- Vital signs (temperature, DBP, SBP, pulse) recorded after at least 5 minutes in the supine position. If the Investigator considers that any of the vital signs measurements are clinically significant, these parameters may be repeated at least 5 minutes later. If any of them remain clinically significant the subject will be discontinued from the study.
- Urine drug screen and alcohol breath test
- Physical examination
- Collect 10-mL blood sample for immunogenicity testing (e.g., HAI testing)

- Collect 50-mL blood sample for generation of PBMCs for cellular responses to the vaccine (cytotoxicity, cytokine, chemokine release).
- Collect a nasopharyngeal swab and process per standard methods
- Administer the influenza vaccine (0.5 mL in deltoid muscle)

The following activities and/or assessments will be performed on each of the study days.

Day 4 \pm 1

- Record concomitant medications
- AE monitoring
- Limited physical examination, if needed
- Collect 10-mL blood sample for immunogenicity testing (e.g., HAI)

Day 8 \pm 1

- Record concomitant medications
- AE monitoring
- Limited physical examination, if needed
- Collect 10-mL blood sample for immunogenicity testing (e.g., HAI)
- Collect 50-mL blood sample for generation of PBMCs for cellular responses to the vaccine

Day 15 \pm 1

- Record concomitant medications
- AE monitoring
- Limited physical examination, if needed
- Collect 10-mL blood sample for immunogenicity testing (e.g., HAI)

Day 29 \pm 1

- Record concomitant medications
- AE monitoring
- Limited physical examination, if needed
- Collect 10-mL blood sample for immunogenicity testing (e.g., HAI)
- Collect a nasopharyngeal swab and process per standard methods

Day 91 \pm 10

- Record concomitant medications
- AE monitoring
- Limited physical examination, if needed
- Collect 10-mL blood sample for immunogenicity testing (e.g., HAI)

Day 181 \pm 10

- Record concomitant medications
- AE monitoring
- Limited physical examination, if needed

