
 To evaluate the mucosal immune response NasoVAX when administered by intranasal spray at a single dose of 1×10^9, 1×10^{10}, or 1×10^{11} vp 	
 Immunoglobulin A (IgA) antibody level measured by enzyme-linked immunosorbent assay (ELISA): 
 GMT GMR

 To evaluate the humoral immune response against nonrepresented influenza strains after NasoVAX administration 	
 Antibody level measured by HAI and MN in serum against each strain tested: 
 GMT GMR Responder rate: the number and percentage of subjects with 2-fold and 4-fold rise since baseline

 To evaluate the effect of predose adenovirus serotype 5 (Ad5) serum antibody levels on the immunogenicity of NasoVAX 	
 Predose Ad5 antibody GMT measured by MN in serum Day 29 GMR and responder rate from antibody level measured by HAI in serum

 To compare immunogenicity results to those obtained from banked samples from a previous study of licensed seasonal vaccine in a similar subject population (ALT-FLZ-401) 	
 Antibody level measured by HAI in serum: 
 GMT GMR SPR SCR Antibody level measured by MN in serum: 
 GMT Responder rate SFUs to hemagglutinin peptides measured by ELISpot in PBMCs: 
 Geometric mean SFUs Responder rate IgA antibody level measured by ELISA: 
 GMT GMR

4 Study Design

Study ALT-103-201 is a Phase 2a, randomized, double-blind, placebo-controlled trial to evaluate the safety, and immunogenicity of NasoVAX in healthy adults 18 to 49 years of age. Subjects will be screened within 28 days of randomization (Day 1). Approximately 60 subjects who meet all inclusion and no exclusion criteria and provide written informed consent will be enrolled into 3 sequential cohorts of 20 subjects each defined by the viral particle dose (1×10^9 , 1×10^{10} , and 1×10^{11} vp). Within each cohort and its sentinel group, subjects will be randomized in a 3:1 ratio to receive 1 intranasal dose of NasoVAX or placebo (Day 1) as shown in Table 4-1.

Table 4-1 NasoVax Study Design

Cohort	Dose (vp)	Number of Subjects	
		NasoVAX	Placebo
1	1×10^9	15	5
2	1×10^{10}	15	5

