3	1×10^{11}	15	5
Study Total Target		45	15
Total		60	

A sentinel group of 5 subjects from each cohort will be dosed. Dosing of the remainder of each cohort may proceed after the last sentinel subject completes Day 8 if no events meeting stopping criteria have occurred. The Safety Review Committee (SRC), consisting of the Investigator, the Medical Monitor, and a Sponsor Representative, will review AE, reactogenicity, and laboratory data through at least Day 8 for all subjects in each cohort before subjects are randomized to the next higher dose. If any event meeting stopping criteria occur, the SRC will review all available safety information before additional patients are dosed. Stopping criteria are as follows, using the Food and Drug Administration (FDA) toxicity grading scale [1]:

- Occurrence of any related SAE or Grade 4 AE
- Occurrence of 2 Grade 3 AEs in the same organ system
- Occurrence of the same Grade 3 laboratory abnormality in 2 or more subjects

Each subject will record local events, systemic events, and oral temperature in a diary daily for 14 days after the NasoVAX/placebo dose. Each subject will be contacted by telephone on Day 2 for safety assessment and review of the diary. Subjects will return to the investigational site on Days 4, 8, 15, 29, 91, and 181 for safety and immunogenicity assessments.

A serum sample will be collected from each subject for evaluation of influenza HAI assay against A/California/04/2009 predose on Day 1 on Days 4, 8, 15, 29, 91, and 181; Ad5 antibody, MN assay against both A/California/04/2009(H1N1) and nonrepresented strains, and HAI against nonrepresented strains will also be evaluated at Days 1 and 29. A whole

blood sample will be collected from each subject and processed to isolate PBMCs for evaluation of T-cell responses by ELISpot predose on Day 1 and on Day 8.

A nasopharyngeal swab sample will be collected from each subject at Screening and on Days 4, 8, 15, 29, and 91 to measure concentration of the Ad5 vector for assessment of vaccine vector shedding by quantitative polymerase chain reaction (qPCR) assay. Once a negative result is obtained, later samples may not be tested. ELISA for measurement of IgA will also be performed on the swab samples from Screening and Day 29 for evaluation of mucosal immune response.

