7.4.10 Baseline Values

Baseline values are the values obtained prior to the vaccination on Day 1. If the baseline value is missing, the value at Screening will be treated as the baseline.

8 Summary of Study Data

For all summaries described below, subjects enrolled in the ALT-103-201 and randomized to an active dose will be summarized/listed under the heading "NasoVAX", while subjects enrolled in ALT-FLZ-401 will be summarized/listed under the heading "Fluzone".

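### The nasal IgA baseline is a Screening swab in ALT-103-201 but a Day 1 predose swab in ALT-FLZ-401, although the SAP says the immunogenicity schedules match

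*SAP*

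**What the plan says.** SAP Section 4 presents ALT-FLZ-401 as a sample set built to resemble that of ALT-103-201, and states: "The same site, entry criteria and schedule of assessments for immunogenicity were followed".

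For ALT-103-201, the same section says "A nasopharyngeal swab sample will be collected from each subject at Screening and on Days 4, 8, 15, 29, and 91", and then "ELISA for measurement of IgA will also be performed on the swab samples from Screening and Day 29 for evaluation of mucosal immune response". Table 4-2 agrees: it has no swab on Day 1, Screening runs from Day -28 to Day -1, and the Day 29 window is ±3 days.

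For ALT-FLZ-401, Protocol Section 6.3.1 lists, among the Day 1 procedures before the vaccine is given, "Collect a nasopharyngeal swab and process per standard methods". The protocol synopsis gives the same order. SAP Table 4-3 marks swabs on Day 1 and Day 29 only, with a Day 29 window of ±1 day.

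SAP Section 7.4.10 defines baseline as the value before vaccination on Day 1 and adds: "If the baseline value is missing, the value at Screening will be treated as the baseline". Table 8-1 marks nasal IgA for GMT, for GMR and for comparison with ALT-FLZ-401. Section 8.6 fits an ANCOVA with log baseline as covariate and contrasts each NasoVAX dose group with placebo and, where applicable, with Fluzone.

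**The concern.** The comparison with Fluzone is neither randomised nor contemporaneous. Its credibility rests largely on the claim that the two studies collected samples in the same way. For nasal IgA the SAP's own tables contradict that claim, and the SAP does not mention the difference.

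Section 7.4.10 makes the difference easy to miss. The Screening value reads like a rescue for the occasional missing sample. For IgA in ALT-103-201 it applies by design to every subject, about 60 in all. In ALT-FLZ-401 it cannot apply, because no swab is taken at Screening.

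At stake is the meaning of two planned results: the IgA GMR set beside that of Fluzone, and the ANCOVA ratio of each NasoVAX dose to Fluzone. Both use baseline, and Section 7.4 tests at two-sided 0.05 without multiplicity adjustment. A change that happened before dosing could be read as a difference between products.

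**Working it through.** The SAP gives no figure on this point to reproduce. The check sets the two schedules side by side, counts days, and follows the baseline into the two analyses.

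**Schedules**

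| Item | ALT-103-201 (SAP Section 4, Table 4-2) | ALT-FLZ-401 (Protocol 6.3.1, SAP Table 4-3) |
|---|---|---|
| IgA baseline swab | Screening, Day -28 to Day -1 | Day 1, predose |
| Swab on Day 1 | None | Yes |
| IgA post-vaccination swab | Day 29 ±3 | Day 29 ±1 |
| Serum and PBMC baseline | Day 1 predose | Day 1 predose |

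In the text copy of Protocol Table 15.2 the swab mark appears under Screening, but so does the vaccination, so the columns have shifted. Section 6.3.1, the synopsis and SAP Table 4-3 settle the Day 1 timing.

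**Days from baseline swab to Day 29 swab**

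There is no Day 0. Day d is d − 1 days after dosing, and Day −d is d days before it.

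- ALT-103-201, shortest: Day -1 to Day 26 = 1 + 25 = 26 days.
- ALT-103-201, longest: Day -28 to Day 32 = 28 + 31 = 59 days.
- ALT-103-201 at nominal Day 29: 1 + 28 = 29 to 28 + 28 = 56 days.
- ALT-FLZ-401: Day 1 to Days 28 to 30 = 27 to 29 days; 28 at nominal Day 29.

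The lead from baseline swab to dosing is 1 to 28 days in ALT-103-201 and 0 days in ALT-FLZ-401.

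**Effect on the GMR**

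Let f be the geometric mean ratio of IgA on Day 1 to IgA at Screening in ALT-103-201. It is not measured, because there is no Day 1 swab. Then:

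- ALT-103-201 GMR = Day 29 / Screening = (Day 29 / Day 1) × f.
- Fluzone GMR = Day 29 / Day 1.

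The two are on the same footing only if f = 1.

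**Effect on the ANCOVA**

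With slope β on log baseline, the adjusted difference is (mean log Day 29, NasoVAX − Fluzone) − β × (mean log baseline, NasoVAX − Fluzone). Using Screening in place of Day 1 lowers the NasoVAX baseline mean by log f. That adds β × log f to the difference, so the back-transformed ratio is multiplied by f^β (holding β fixed).

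**Illustration on assumed values**

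The documents give neither f nor β. I assumed f from 0.8 to 1.25 and β from 0.3 to 0.8.

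| f | GMR multiplied by | ANCOVA ratio, β = 0.3 | β = 0.5 | β = 0.8 |
|---|---|---|---|---|
| 0.8 | 0.80 | 0.935 | 0.894 | 0.837 |
| 0.9 | 0.90 | 0.969 | 0.949 | 0.919 |
| 1.1 | 1.10 | 1.029 | 1.049 | 1.079 |
| 1.25 | 1.25 | 1.069 | 1.118 | 1.195 |

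The adjusted comparison moves less than the GMR, but adjustment does not remove the mismatch.

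**What the baseline mismatch leaves alone**

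- The unadjusted Day 29 IgA GMT uses no baseline.
- NasoVAX versus placebo uses Screening swabs on both sides.
- Serum and PBMC baselines are Day 1 predose in both studies.

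The different Day 29 window is a separate departure. It belongs to the visit, so it touches Day 29 serum as well as the swab.

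**The case against.** The best defence is that the consequence is small and the facts are in view. Comparison with ALT-FLZ-401 is one exploratory objective. Both schedules are printed in full, Section 7.4.10 expressly allows a Screening baseline, and Section 4 already says the studies were not contemporaneous. Aligning the swabs would not remove that limit. All of this stands, and it limits the weight of the point. It does not make the Section 4 statement true for IgA, and allowing a Screening baseline does not make it equivalent to a Day 1 predose one.

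Some stronger readings are tempting, but the documents do not support them.

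- *Colds distort the NasoVAX baseline.* A reader might infer this from Protocol exclusion 13, where "Any symptoms of upper respiratory infection or temperature" above 38°C counts only within 3 days before Day 1. But exclusion 14, on nasal congestion or rhinorrhea, has no time window, and eligibility is checked at Screening too. These criteria are also those of ALT-FLZ-401. The ALT-103-201 protocol is not among the documents, and at least the age limits differ (18 to 49 against 18 to 50). The SAP names no antigen for the IgA ELISA, so an effect of a cold on it cannot be assumed.
- *An infection between Screening and Day 1 raises Day 29 IgA only in NasoVAX subjects.* It could do so in either study. The difference is whether the baseline was taken before or after it.
- *The extra swabs on Days 4, 8 and 15 change Day 29 IgA.* Nothing in the documents says so.
- *Any ALT-103-201 subjects still to be dosed should have a Day 1 swab as baseline.* Cohorts are sequential by dose and placebo is pooled across them. A switch part-way would tie baseline timing to dose and mix baselines within placebo, harming the one IgA contrast that is now sound.

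**Conclusion.** The point holds. For nasal IgA the two studies did not follow the same schedule. The baseline precedes dosing by 1 to 28 days in ALT-103-201 and by 0 days in ALT-FLZ-401, and baseline to Day 29 spans 26 to 59 days against 27 to 29. The IgA GMR and the baseline-adjusted ANCOVA against Fluzone therefore compare unlike quantities.

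The day counts rest only on the printed windows and on there being no Day 0. The size and direction of any bias are unknown. On the assumed values above, the GMR would be multiplied by 0.80 to 1.25 and the ANCOVA ratio by about 0.84 to 1.20; these ranges show sensitivity and are not estimates. A reader might infer that the mismatch favours NasoVAX, or that the Fluzone comparison fails for every assay. The documents support neither: f could lie on either side of 1, and the baseline mismatch is confined to the swab.

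**What to change.** 1. In SAP Section 4, correct the statement on matching schedules. Say that the IgA baseline swab is at Screening in ALT-103-201 and predose on Day 1 in ALT-FLZ-401, and that the Day 29 windows are ±3 and ±1 days.
2. In Section 8.6, let the randomised NasoVAX-versus-placebo contrast carry inference for IgA. Report the IgA GMR and ANCOVA against Fluzone descriptively, with the baseline difference stated beside them.
3. Add one sensitivity table for IgA: the unadjusted Day 29 GMT ratio of each NasoVAX dose group to Fluzone, and the ALT-103-201 results by interval from Screening swab to dose. Show the interval as it falls. The documents give no basis for a fixed cut-off, and with 15 subjects per dose group a subset could be very small.

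The cost is a few lines of SAP text and one table from dates already held. No sampling changes. The downside is a weaker claim for one exploratory comparison.
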